8.3.2. Pregnancy

Collection of pregnancy information

Male participants with partners who become pregnant

The investigator will attempt to collect pregnancy information on any male participant's female partner who becomes pregnant while the male participant is in this study. This applies only to male participants who receive LY3561774.

After learning of a pregnancy in the female partner of a study participant, the investigator will obtain a consent to release information from the pregnant female partner directly, and within 24 hours after obtaining this consent will record pregnancy information on the appropriate form and submit it to the sponsor.

The female partner will also be followed to determine the outcome of the pregnancy. Information on the status of the mother and child will be forwarded to the sponsor. Generally, the follow-up will be no longer than 6 to 8 weeks following the estimated delivery date. Any termination of the pregnancy will be reported regardless of gestational age, fetal status (presence or absence of anomalies) or indication for the procedure.

Female participants who become pregnant

The investigator will collect pregnancy information on any female participant who becomes pregnant while participating in this study. The initial information will be recorded on the appropriate form and submitted to the sponsor within 24 hours of learning of a participant's pregnancy.

The participant will be followed to determine the outcome of the pregnancy. The investigator will collect follow-up information on the participant and the neonate and the information will be forwarded to the sponsor. Generally, follow-up will not be required for longer than 6 to 8 weeks beyond the estimated delivery date. Any termination of pregnancy will be reported, regardless of gestational age, fetal status (presence or absence of anomalies) or indication for the procedure.

While pregnancy itself is not considered to be an AE or SAE, any pregnancy complication or elective termination of a pregnancy for medical reasons will be reported as an AE or SAE.

A spontaneous abortion (occurring at <20 weeks gestational age) or still birth (occurring at ≥20 weeks gestational age) is always considered to be an SAE and will be reported as such.

Any post-study pregnancy-related SAE considered reasonably related to the study intervention by the investigator will be reported to the sponsor as described in Section 8.3.1. While the investigator is not obligated to actively seek this information in former study participants, he or she may learn of an SAE through spontaneous reporting.

Any female participant who becomes pregnant while participating in the study will be withdrawn from the study. If the participant is discontinued from the study, follow the standard discontinuation process and continue directly to the follow-up phase. The follow-up on the pregnancy outcome should continue independent of intervention or study discontinuation.

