Visits	1	2	3	4	5	6	7	8	9	10	11	12	ED	801	ED = early discontinuation.
Days from randomization	-45	0	15	30	60	90	120	150	180	210	240	270	—	360	
Visit interval tolerance (days)		—	±3	±3	±3	-5 to +10	±7	±7	±7	±7	±7	±7	—	±7	Visit 1 procedures may be conducted over more than 1 day if all activities are completed within the allowable visit tolerance.
Fasting Visit	X	X	X	X	X	X	X	X	X	X	X	X	X	X	Participants should not eat or drink anything but water for 8 hours before the visit. If a participant arrives not fasted, schedule the laboratory draw for another date.
Symptom- directed physical assessment		X		X	X	X	X	X	X	X	X			X	Performed by qualified personnel per local regulations based on participant status and standard of care.
Single 12-lead ECG (local)	X					X			X			X	X	X	Collect at least 30 minutes prior to collection of blood samples for laboratory testing, including PK samples. Participants should be supine for approximately 5 to 10 minutes before ECG collections and remain supine but awake during the ECG collection. ECGs may be repeated at the investigator’s discretion at any visit.
Schedule MRI	X														Schedule MRI prior to randomization for applicable participants who meet screening inclusion and exclusion criteria.
MRI		X							X				X		Performed for the quantification of hepatic fat. See Section 8.2.4. The participant must fast for at least 6 hours prior to the MRI. If they did not fast, schedule MRI for another date prior to randomization.

Study J3F-MC- EZCB(e)	Screening	Double-Blind Treatment and Assessment											Follow-up	Comments	
		1	2	3	4	5	6	7	8	9	10	11			12
Remote Visits			X	X	X		X	X		X	X				V801 on-site for all sites including the US
Visits	1	2	3	4	5	6	7	8	9	10	11	12	ED	801	ED = early discontinuation.
Days from randomization	-45	0	15	30	60	90	120	150	180	210	240	270	—	360	
Visit interval tolerance (days)		—	±3	±3	±3	-5 to +10	±7	±7	±7	±7	±7	±7	—	±7	Visit 1 procedures may be conducted over more than 1 day if all activities are completed within the allowable visit tolerance.
Fasting Visit	X	X	X	X	X	X	X	X	X	X	X	X	X	X	Participants should not eat or drink anything but water for 8 hours before the visit. If a participant arrives not fasted, schedule the laboratory draw for another date.
															Visit 2: Perform MRI at any day prior to randomization. ED Visit: if ED Visit is prior to Visit 9, then conduct MRI. If ED Visit is after Visit 9, do not conduct MRI.

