7.1. Discontinuation of Study Intervention

When necessary, a participant may be permanently discontinued from study intervention.

Situations when discontinuation of study intervention may occur

A participant should be permanently discontinued from study intervention if

- the participant becomes pregnant during the study
- a prohibited treatment listed in Section 10.7.3 is initiated during the study, or
- in the opinion of the investigator, the participant should permanently discontinue the study intervention for safety reasons.

If the investigator determines that a systemic hypersensitivity reaction has occurred related to study intervention administration, the participant may be permanently discontinued from the study intervention, and the sponsor's designated medical monitor should be notified. If the investigator is uncertain about whether a systemic hypersensitivity reaction has occurred and whether discontinuation of study intervention is warranted, the investigator should consult the sponsor.

If study intervention is permanently discontinued, the participant will remain in the study and follow procedures for the remaining study visits as shown in the SoA.

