7.2. Participant Discontinuation/Withdrawal from the Study

A participant may withdraw from the study:

- at any time at the participant's own request
- at the request of the participant's designee (for example, parents or legal guardian)
- at the discretion of the investigator for safety, behavioral, compliance, or administrative reasons
- if enrollment in any other clinical study involving an investigational product or enrollment in any other type of medical research judged not to be scientifically or medically compatible with this study
- if the participant, for any reason, requires treatment with a therapeutic agent that is prohibited by the protocol and has been demonstrated to be effective for treatment of the study indication. In this case, discontinuation from the study occurs prior to introduction of the new agent.

Discontinuation is expected to be uncommon.

At the time of discontinuing from the study, if possible, the participant will complete procedures for an early discontinuation visit and safety follow-up, if applicable, as shown in the SoA. See SoA for data to be collected at the time of study discontinuation and follow-up and for any further evaluations that need to be completed. The participant will be permanently discontinued from both the study intervention and the study at that time.

If the participant withdraws consent for disclosure of future information, the sponsor may retain and continue to use any data collected before such a withdrawal of consent. If a participant withdraws from the study, the participant may request destruction of any samples taken and not tested, and the investigator must document this in the site study records.

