10.10. Appendix 10: Protocol Amendment History

The Protocol Amendment Summary of Changes Table for the current amendment is located directly before the Table of Contents (TOC).

Amendment [d]

This amendment is considered to be nonsubstantial.

Overall Rationale for the Amendment:

The rationale for the amendment is to clarify how to maintain the blind during IMP administration.

Section # and Name	Description of Change	Brief Rationale
5.1. Inclusion Criteria	Corrected second WOBCP acronym to be consistent with Section 10.4.1	Accuracy
6.3. Measures to Minimize Bias: Randomization and Blinding	One sentence changed to clarify what third party will be responsible for to maintain the blind. Additional sentences added to clarify lower risk of unblinding and administering IMP.	Clarification

Amendment [c]

This amendment is considered to be substantial because it is likely to have a significant impact on the reliability and robustness of the data generated in the clinical study.

Overall Rationale for the Amendment:

This amendment includes protocol revisions in response to FDA feedback and request for changes for Sections 7.1, 9.4, and 10.4.1. Additional changes to the protocol and the corresponding rationale for the changes are detailed in the table below.

Section # and Name	Description of Change	Brief Rationale
7.1. Discontinuation of Study Intervention	Changed text to state that participants will remain in the study and follow procedures for the remaining study visits.	FDA feedback and request.
8.3.5. Major Adverse Cardiovascular Events (MACE)	Added cardiogenic shock due to myocardial infarction and resuscitated sudden death to the list of adjudicated events.	To match the Adjudicated Report & Charter.
9.4. Interim Analysis	
 • Added information about planned interim analyses. • Moved text that states that the SAP will describe the interim analysis in greater detail up near the new text about the planned interim analyses. • Added text for unplanned interim analysis. • Removed text that was no longer relevant. 	
 • FDA feedback and request • Better readability, and • Updates per Lilly policy.

Section # and Name	Description of Change	Brief Rationale

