(Treatmen t k vs. Reference Arm)	SE	$e^{\bar{Z}_{b}} \sqrt{e^{2\hat{\mu}_{\Delta Z,k}} \cdot \left(\widehat{SE}_{\Delta Z,k}\right)^2 + e^{2\hat{\mu}_{\Delta Z,R}} \cdot \left(\widehat{SE}_{\Delta Z,R}\right)}$	$\exp(\hat{\mu}_{\Delta Z, k \ vs \ R}) \cdot \widehat{SE}_{\Delta Z, k \ vs \ R} \times 100$
12)	P-value	NR	P∆Z,k vs R
	95% CI	Estimate $\pm \Phi^{-1} (1 - \frac{\alpha}{2}) * SE$	$(\left[\exp\left(L_{\Delta Z,k\ vs\ R}\right)-1\right]\times 100, \left[\exp\left(U_{\Delta Z,k\ vs\ R}\right)-1\right]\times 100)$

Abbreviation: CI = confidence interval; NR = not reported; SE = standard error.

In general, a time-averaged parameter will refer to the area under the curve (AUC) constructed using the trapezoidal rule, applied to the parameter according to the scheduled time, divided by the length of observation. For example, a time-averaged dependent variable for Days 30 to 180 will equal AUC/150, where AUC represents the AUC constructed by the trapezoidal rule.

Unless otherwise specified, baseline is defined as the last non-missing measurement recorded on or before the randomization visit, prior to first dose of intervention.

When considering treatment-emergent abnormal safety laboratory values and vital signs, baseline observation will start from the screening visit and end prior to, or at, the randomization visit, wherein all scheduled and unscheduled measurements will be included. The baseline for the treatment-emergent safety analysis will be the maximum/minimum from all measurements taken during the baseline period. For postbaseline measurements, all scheduled and unscheduled measurements in the analysis period will be included. The maximum/minimum from all measurements taken during the analysis period will be used in the treatment-emergent safety analysis. The end of Study EZCB participation for a participant will be the earliest of date of death, the date of withdrawal from further participation in the study, or the date of the safety follow-up visit (Visit 801). For participants considered to be lost to follow-up, end of Study EZCB participation will be the date participant is lost to follow-up as reported by the investigator. Participant data included in the database after the last date of Study EZCB participation (including the safety follow-up period) will be excluded from statistical analysis.

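### Protocol 8.3.2 withdraws pregnant participants, and 7.2 exits those needing an effective prohibited lipid drug, while 7.1 keeps participants for all remaining visits once study drug stops

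*Protocol*

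**What the plan says.** Protocol 7.1 names pregnancy, and the start of a treatment prohibited in 10.7.3, among the reasons for permanently stopping study intervention. After such a stop, "the participant will remain in the study and follow procedures for the remaining study visits", as set out in the SoA. No exception is given. Section 10.7.3 agrees: if a prohibited treatment is needed, the intervention is stopped, and nothing is said about leaving the study.

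Two other places send the same people out of the study:

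- Protocol 8.3.2: "Any female participant who becomes pregnant while participating in the study will be withdrawn from the study". The next sentence, on a participant who is discontinued from the study, says to "follow the standard discontinuation process and continue directly to the follow-up phase".
- Protocol 7.2, last bullet, on a participant who needs a prohibited agent of proven effect in the study indication: "In this case, discontinuation from the study occurs prior to introduction of the new agent". Section 7.2 adds that study discontinuation ends both the intervention and the study.

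The amendment history (10.10) shows that the 7.1 rule came in with amendment (c) at FDA request: "Changed text to state that participants will remain in the study and follow procedures for the remaining study visits". That amendment's table lists no matching change to 7.2 or 8.3.2.

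**The concern.** The same event leads to opposite instructions, and no text says which prevails. Two sites could handle the same pregnancy in opposite ways and both be following the protocol.

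Two things are at stake. The first is safety observation. Both documents compare safety whether or not dosing continued. Protocol 2.3.1 names hepatobiliary events as a potential risk and relies on repeated liver-enzyme monitoring. In Phase 1 the pharmacodynamic effect was still present at the last sample, Day 169 (Protocol 2.2), so someone who leaves at Day 90 may still be under drug effect.

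The second is the treatment-regimen estimand in SAP 1.1. Its treatment-policy strategy calls for lipid values observed after study drug stops. A participant who must leave before starting, say, a fibrate cannot supply them.

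**Working it through.** **The rules side by side**

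| Event | 7.1 | 10.7.3 | Conflicting text |
|---|---|---|---|
| Pregnancy | Stop drug, stay for SoA visits | not covered | 8.3.2: withdrawn from study |
| Prohibited agent effective for dyslipidemia | Once started: stop drug, stay | Once needed: stop drug | 7.2: exit before the agent starts |

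The first row is a plain contradiction. In the second row the triggers differ between 7.1 (started) and 7.2 (needed), but 10.7.3 also uses need as its trigger and stops only the drug. So 7.2 is out of line even on its own trigger. This row covers only prohibited lipid agents; statins (except simvastatin 80 mg), PCSK9 inhibitors, bempedoic acid and ezetimibe are permitted.

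**Scheduled contacts lost**

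From the SoA, post-randomization Visits 3 to 12 number 10. Each includes AE review, chemistry with liver enzymes, coagulation, lipids and ApoB. Visit 801 applies only if ApoB is still below 80% of baseline at Day 270. After an early exit, at most one early discontinuation (ED) visit and one Visit 801 replace what is lost, so net loss = visits forgone − 2.

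| Case | Forgone (with Visit 801) | Net of ED and Visit 801 | If neither takes place |
|---|---|---|---|
| Exit at Visit 6, Day 90 | Visits 7–12: 6 (7) | 6 − 2 = 4 to 7 − 2 = 5 | 6 to 7 |
| Exit at Visit 9, Day 180 | Visits 10–12: 3 (4) | 3 − 2 = 1 to 4 − 2 = 2 | 3 to 4 |
| Hematology, ECG, ADA only, exit at Day 90 | Visits 9, 12: 2 (3) | 2 − 2 = 0 to 3 − 2 = 1 | 2 to 3 |

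The loss therefore falls mainly on AE review, liver enzymes and lipids. The protocol does not say when Visit 801 falls after an early exit. If it stays at Day 360, the scheduled gap after a Day 90 exit is 360 − 90 = 270 days, against 30 days between visits up to Day 270 under 7.1.

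**Whether the offsets reach the analysis**

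- The ED visit takes place only where possible. SAEs after participation ends are reported only if judged possibly related (Protocol 8.3.1).
- Pregnancy follow-up is itself unclear: the 8.3.1 table stops collection 4 days after the last dose, while 8.3.2 covers pregnancies throughout participation.
- SAP 4.1 ends participation at "the earliest of date of death, the date of withdrawal from further participation in the study", or Visit 801. Data "after the last date of Study EZCB participation (including the safety follow-up period) will be excluded from statistical analysis". This leaves open whether a Visit 801 held after withdrawal counts.
- Withdrawal does not spare procedures. The SoA says "if ED Visit is prior to Visit 9, then conduct MRI", with no exception for pregnancy.

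**Efficacy**

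SAP 4.5.2 analyses the FAS with multiple imputation, under missing at random according to SAP 4.1. For the 7.2 group, forced exit turns values that could have been observed on the new agent into values that must be imputed.

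The primary MMRM uses only data from before intercurrent events, and stopping drug or starting a prohibited agent is such an event. The plan's power figure is not in dispute and reproduces: 175 at 2:1:2:2 gives 50/25/50/50 randomized; multiplied by 0.8, that is 40/20/40/40 completers. With a difference of 30, SD 15 and two-sided alpha 0.05, power exceeds 0.9999 for both 40 vs 20 and 40 vs 40.

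**The case against.** The 7.2 list opens permissively and can be read as an allowed exit for a narrow case, with 7.1 as the general rule. Likewise, 8.3.2 can be read as a specific exception to 7.1, since its next sentence is conditional; the defect is then a missing cross-reference. Whether to keep a pregnant participant is the sponsor's choice.

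The Day 169 effect concerns ANGPTL3, TG and LDL-C, not liver safety. The plasma half-life is hours, and the Phase 1 enzyme elevations after single doses were transient. Known events are not dropped at exit: Protocol 8.3 keeps the investigator responsible for serious, related or discontinuation-causing events, and 8.2.6 continues liver-test monitoring until values settle. The 270-day gap assumes Visit 801 stays at Day 360, although 8.3.2 sends participants directly to follow-up. The safety set includes follow-up, and retention would also bring an MRI at Visit 9.

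Much of this stands. The 7.2 limb is the weaker one, the 270-day gap is conditional, the lipid effect does not prove continuing liver risk, and the MRI needs an exception under either rule. The log's silence on 7.2 and 8.3.2 does not prove an oversight. But following known events does not restore scheduled detection of new ones, and no offset supplies the later lipid values. Even on the exception reading, 7.1 must say so.

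**Conclusion.** The concern holds. The pregnancy rules in 7.1 and 8.3.2 contradict each other in current text, and the last bullet of 7.2 departs from 7.1 and 10.7.3. Following 8.3.2 or 7.2 as written gives up scheduled safety data, and for the 7.2 group treatment-regimen data, that 7.1 and the SAP call for. Per participant leaving at Day 90, the cost is a net 4 to 5 contacts, or 6 to 7 without the two replacement visits.

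The number affected is not given and is probably small. Non-abstinent women of childbearing potential need two contraceptive methods. Sites see no post-randomization lipid panel and only the Day 270 ApoB, so little would prompt a new agent. Section 7.2 itself expects few discontinuations. The size of any bias in the FAS analysis cannot be derived from the documents.

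The primary and secondary EAS analyses and the power are essentially unaffected. This assumes the event is recorded as an intercurrent event. SAP 4.1 treats a participant with both doses as on treatment throughout, so a pregnancy exit between the second dose and Day 180 could in principle cost an EAS value.

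**What to change.** - **Protocol 8.3.2:** pregnancy stops the intervention; the participant stays for safety visits and AE collection. Omit procedures unsuitable in pregnancy, such as the MRI at Visit 9 or at an ED visit if she leaves earlier.
- **Protocol 7.2, last bullet:** needing such an agent stops the intervention only. Visits, laboratory draws and AE collection continue under 7.1 unless consent is withdrawn.
- **Fallback:** if the sponsor has a reason to keep withdrawal for pregnancy, name it in 7.1 as an exception and state when Visit 801 falls after early exit. One sentence in SAP 4.1 should then say whether that visit's data count.

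The cost is wording in two protocol sections and a clarification to sites. The recommended change adds no visits beyond the SoA and needs no SAP change, because the FAS already uses observed data regardless of adherence and imputes only what is missing. A pregnant participant would be asked to attend more visits than under 8.3.2, but could still withdraw at her own request.

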8.3.3. Hypersensitivity Reactions

Many drugs, including oral agents and biologic agents, carry the risk of systemic hypersensitivity reactions. If such a reaction occurs, additional data should be provided to the sponsor in the designated CRFs.

Sites should have appropriately trained medical staff and appropriate medical equipment available when study participants are receiving study intervention. It is recommended that participants who experience a systemic hypersensitivity reaction be treated per national and international guidelines.

In the case of a suspected systemic hypersensitivity event, additional blood samples should be collected as described in Section 10.2.1. Laboratory results are provided to the sponsor via the central laboratory.

8.3.4. Injection-Site Reactions

Symptoms and signs of a local ISR may include erythema, induration, pain, pruritus, and edema.

If an ISR is reported by a participant or site staff, the ISR CRF will be used to capture additional information about this reaction, for example, injection-site pain, degree and area of erythema, induration, pruritus, and edema.

At the time of ISR occurrence, collect an immunogenicity and PK sample.

8.3.5. Major Adverse Cardiovascular Events (MACE)

Nonfatal cardiovascular AEs will be adjudicated by a committee of physicians external to Lilly with cardiology expertise. This committee will be blinded to treatment assignment.

The nonfatal cardiovascular AEs to be adjudicated include

- myocardial infarction
- cardiogenic shock due to myocardial infarction
- hospitalization for unstable angina
- hospitalization for heart failure
- coronary interventions (such as coronary artery bypass graft or percutaneous coronary intervention)
- resuscitated sudden death, and
- cerebrovascular events, including cerebrovascular accident (stroke) and transient ischemic attack.

